7.1 Study Subjects

7.1.1 Disposition of Subjects

The number of enrolled subjects at each cohort, and the compliance at each scheduled visit will be summarized. The number of discontinuations (if any) and reason for discontinuation and whether they occurred before a specific scheduled visit will be summarized.

7.1.2 Clinical Investigation Plan (CIP) Deviations

Summaries of major, minor, and COVID-19 impacted protocol deviations will be provided by cohort.

7.1.3 Analysis Sets

Intent-to-Treat (ITT): For this study, all subjects who sign the written informed consent and also have the study stent (Resolute Onyx stent™) introduced into the guide catheter will be counted in the ITT set, which will be the primary analysis set.

Per-Protocol (PP): The ITT set excluding subjects who do not meet certain key entry criteria (for exclusion criteria below, if any answer is “yes”, the patients are excluded from PP population):

1. Did not receive any study device
2. Received study device, and another type of DES
3. Did not meet the following inclusion criteria:
 - a. Inclusion 2: Must have symptomatic coronary artery disease; chronic stable angina, silent ischemia, and acute coronary syndromes including non-ST elevation myocardial infarction and ST-elevation myocardial infarction.
 - b. Inclusion 7: Subject requires treatment of one or more target lesion(s) amenable to treatment with a Resolute Onyx™ 2.0 mm – 5.0 mm stent in up to two separate target vessels
4. Did not meet the following exclusion criteria:
 - a. Exclusion 3: Subjects who are judged to have a lesion that prevents complete inflation of an angioplasty balloon or proper placement of the stent or stent delivery system
 - b. Exclusion 4: Unprotected left main coronary artery disease (no patent bypass graft(s) to one or more branches of the left coronary artery; the left anterior descending or circumflex artery, with an obstruction greater than 50% in the left main coronary artery)
 - c. Exclusion 5: Subjects with planned PCI of three vessel disease (includes staged procedures)
 - d. Exclusion 6: Currently participating in an investigational drug or another device study that has not completed the primary endpoint or that clinically interferes with the current study endpoints

Note: Studies requiring extended follow-up for products that were investigational, but have since become commercially available, are not considered investigational studies.

In addition to the general exclusion criteria listed above, Bifurcation subjects will be in the PP set only if all the Bifurcation target lesions meet the below criteria:

1. Proximal optimization technique was performed after provisional stenting
2. Baseline side branch diameters per site estimation are ≥ 2.0 mm
3. No planned two stent technique (main and side branch) of a bifurcation

The primary endpoint will also be analyzed in both ITT and PP population.

7.1.4 Pooling of Bifurcation Cohort and bifurcated lesions from Primary/XLV Cohorts

It is intended to pool the two cohorts (Bifurcation Cohort and bifurcation subset from Primary/XLV cohorts). Comparability between the two cohorts on baseline characteristics and on the primary endpoint will be assessed.

- **Covariate homogeneity**

The first step will be to assess the homogeneity of the covariates between two cohort populations. The two-sample t-test or Fisher's exact test will be used depending on the distributions of the covariates. The covariates that will be considered include: lesion length, baseline RVD, age, sex, diabetes, history of MI and worst Canadian Cardiovascular Society angina class. Statistical non-significance (significance level set at 0.15) for any of the covariates is supportive evidence of the comparability of the cohorts without adjusting for that covariate. However, any covariate for which the group difference is deemed to be clinically and statistically significant could be adjusted by using propensity scores as discussed below to account for any covariate imbalances.

- **Outcome Comparability**

If any of the above baseline covariates is significantly different, then the outcome of 12 months TVF rate between the two cohorts will be compared as the following: for each individual a propensity score will be calculated using logistic regression, with indicator for cohort (Bifurcation cohort, bifurcation subset from Primary/XLV cohorts) membership as the dependent variable and the above mentioned covariates as the independent variables (covariates will be included regardless of whether or not they are deemed homogenous). Patients will then be categorized into quintiles based on this propensity score. The 85% confidence interval of propensity score quintile adjusted difference between cohorts in TVF at 12 months will be calculated. If the 85% confidence interval contains zero (0), then the two cohorts will be considered poolable.

If the two cohorts are deemed suitable for pooling based on this analysis, then combined data from the two cohorts will be used to compared to the performance goal. If the data from the two cohorts are not poolable, then Medtronic will discuss with FDA on the next steps.

7.2 General Methodology

All statistical analyses will be performed using Statistical Analysis Software (SAS) for Windows (version 9.1 or higher) or other widely accepted statistical or graphical software. Subject data listings and tabular and graphical presentations of results will be provided.

All analyses will be based on “intent to treat” (ITT) principle, unless otherwise specified. For clinical events, the numerator of the event rate will be the number of “ITT” subjects having an event by the time of interest. The denominator will be the number of subjects who either have an event by the time of interest or have follow-up information beyond the lower window of the follow-up.

The Clinical Study Report will be available for the primary endpoint and for secondary endpoints annually through study close-out at 3 years.

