10.14.1 Study Exit

A study exit eCRF is required for all subjects. Prior to exiting a subject from the study, it is recommended to follow the subject until all ongoing system and/or procedure related AEs are resolved or unresolved with no further actions planned. Following exit, subjects will continue to receive standard medical care. Upon exiting from the study, no further study data will be collected, or study visits will occur for the subject. All data available through the time of the subject's exit will be used for analysis.

Subjects are urged to remain in the study as long as possible but may be exited from the study for any of the following situations:

- Study completed
- Subject lost to follow-up
- Subject death
- Subject did not meet inclusion/exclusion criteria
- Subject was not implanted with a (investigational) device
- Subject did not provide consent

- Subject chooses to withdraw (e.g., consent withdrawal, relocation to another geographic location)
- Investigator deems withdrawal necessary (e.g., medically justified, inclusion/exclusion criteria not met, failure of subject to maintain adequate study compliance)

The following information is required to be collected at study exit:

- Reason for exit

If discontinuation is because of safety or lack of effectiveness, the subject shall be asked to be followed for collecting safety data outside the clinical investigation.

10.14.2 **Study Completed**

At the completion of the 36-month follow-up visit, subjects will be exited from the study. The 36-month follow-up visit and exit visit should be combined, and both a 36-month follow-up CRF and a Study Exit CRF need to be completed.

10.14.3 **Lost to Follow-up**

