14.2.3 Bifurcation cohort

If the 12-month TVF rate is shown to be significantly less than 24.5% for the RESOLUTE ONYX Bifurcation Cohort, then the Bifurcation Cohort will be considered to have met its primary endpoint. Therefore, the null and the alternative hypotheses are:

$$H_0: P_{TVF} \geq 24.5\%;$$

$$H_a: P_{TVF} < 24.5\%$$

where P_{TVF} is the true primary endpoint rate for the study stent. Rejection of the null hypothesis will signify that the PG is met. This PG is based on review of clinical evidence from published literature.

Assuming a one-side alpha level of 0.05 and a true event rate of 16.3%, an effective sample size of 180 subjects will yield 85% power to reject the null hypothesis. Assuming 10% loss to follow-up rate, a total sample size of 200 subjects will be needed; hence data on a total of 200 subjects will be generated.

The expected rate for the RESOLUTE ONYX Bifurcation Cohort was obtained by utilizing the weighted average of outcomes from the RESOLUTE All-Comers (RAC) study⁸ in patients with single bifurcations treated with single or double stents (excluding unprotected left main lesions and patients with three vessel disease), and the from the provisional stenting arm of the TRYTON study.⁹ The weighted average is shown in Table 8.

Table 8: Expected 12-month TVF rate for the RESOLUTE ONYX Bifurcation Cohort

Study/Arm	Stent Used	N	12m TVF Rate
RAC (Resolute Arm) - single bifurcation treatment	ZES	133	11.6%
RAC (Xience V Arm) - single bifurcation treatment	EES	136	12.2%
TRYTON – Provisional Stenting Arm*	DES	339	13.9%**
Weighted Average		13.0%	

* Data from TRYTON SSED
**Adjusted downwards from 15.3% to 13.9% to account for the difference in true versus non-true bifurcated lesions per Medina Classification that were treated in the Resolute All comer study and the provisional stenting arm of the TRYTON study

The performance goal of the RESOLUTE ONYX Bifurcation Cohort of 24.5% represents a clinically acceptable 50% extension from the expected rate as shown in Table 9.

Table 9:Performance Goal

Sample Size	Expected Rate	Margin (50%)	PG	Power
200 (180 evaluable)	16.3%	8.2%	24.5%	≥ 85%

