6.1 Primary Cohort

If the 12-month TLF rate of the Resolute Onyx stent™ is shown to be significantly less than 17.5%, then the Primary Cohort will be considered to have met its primary endpoint. In other words, the null and the alternative hypotheses are:

$$H_0: P_{TLF} \geq 17.5\%$$

$$H_1: P_{TLF} < 17.5\%$$

where P_{TLF} is the true primary endpoint rate for the study stent. Rejection of the null hypothesis will signify that the PG is met.

Assuming a one-sided alpha level of 0.05 and a true event rate of 11.3%, an effective sample size of 369 subjects will yield 96% power to reject the null hypothesis. Assuming a 10% loss to follow-up rate, a total sample size of 410 RESOLUTE ONYX Post-Approval Study subjects will be enrolled in the Primary Cohort. An expected event rate of 7.95% was derived from both arms of the RESOLUTE All-Comers (RAC) trial (excluding unprotected left main (UPLM) and PCI of 3 vessels). Modification of 3.31% was added to the expected rate to adjust the difference in MI reporting per third UDMI. This resulted in the expected event rate of 11.3%. The performance goal 17.5% is a 55% extension from the expected event rate of 11.3%.

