6.3 Bifurcation Cohort

If the 12-month TVF rate is shown to be significantly less than 24.5% for the RESOLUTE ONYX Bifurcation Cohort, then the Bifurcation Cohort will be considered to have met its primary endpoint. Therefore, the null and the alternative hypotheses are:

$$H_0: P_{TVF} \geq 24.5\%;$$

$$H_a: P_{TVF} < 24.5\%$$

where P_{TVF} is the true primary endpoint rate for the study stent. Rejection of the null hypothesis will signify that the PG is met. This PG is based on review of clinical evidence from published literature.

Assuming a one-side alpha level of 0.05 and a true event rate of 16.3%, an effective sample size of 180 subjects will yield 85% power to reject the null hypothesis. Assuming 10% loss to follow-up rate, a total sample size of 200 subjects will be needed; hence data on a total of 200 subjects will be generated.

The expected rate for the RESOLUTE ONYX Bifurcation Cohort was obtained by utilizing the weighted average of outcomes from the RESOLUTE All-Comers (RAC) study in patients with single bifurcations treated with single or double stents (excluding unprotected left main lesions and patients with three vessel disease), and the from the provisional stenting arm of the TRYTON study. The weighted average is shown in Table 1. Then the expected rate of 12-month TVF was modified upwards by 3.3% in order to account for the utilization of Third UDMI definition. Therefore, the expected rate of 12-month TVF is 16.3%.

Table 1: Expected 12-month TVF rate for the RESOLUTE ONYX Bifurcation Cohort

Study/Arm	Stent Used	N	12m TVF Rate
RAC (Resolute Arm) - single bifurcation treatment	ZES	133	11.60%
RAC (Xience V Arm) - single bifurcation treatment	EES	136	12.20%
TRYTON – Provisional Stenting Arm*	DES	339	13.9%**
Weighted Average			13.00%
* Data from TRYTON SSED			
**Adjusted downwards from 15.3% to 13.9% to account for the difference in true versus non-true bifurcated lesions per Medina Classification that were treated in the Resolute All comer study and the provisional stenting arm of the TRYTON study			

7. Statistical Methods

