The tipping point analysis will impute the most 12-month TLF-missing status as "yes" so that the one-side upper 95% confidence interval will be less than or equal to the performance goal of 17.5%.

The survival analysis will be used on TLF to assess the censored subjects. The upper bound of 95% confidence interval through 12 months will be used to compare to the performance goal of 17.5%.

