7.9.1.3 Bifurcation Cohort

The count and percentage of subjects with 12-month TVF will be provided. A one-sided upper bound of the 95% CI of the observed 12-month TVF rate will be calculated through binomial (exact) method. If this upper limit of the 95% CI is below 24.5%, the clinical objective will be considered to have been met for the Bifurcation Cohort.

As a supplementary analysis, to account for missing data, subjects who drop out prior to 330 days post-procedure and do not experience TVF will have their 12-month TVF-missing status ("yes"/"no") imputed using the multiple imputation and tipping point analysis.

The multiple imputation approach will use SAS V9 PROC MI. The covariates to be used in the imputation model are lesion-length, baseline RVD, age, sex, diabetes, history of MI, Canadian Cardiovascular Society Angina Class, and TVF status at visits prior to dropout. One hundred imputed data sets will be generated. An overall TVF rate and its one-sided upper 95% confidence intervals will be generated across the one hundred imputed data sets. For the subjects with 2 or more target lesions, the longest lesion length and the smallest baseline RVD will be used in the imputation model.

The tipping point analysis will impute the most 12-month TVF-missing status as “yes” so that the one-side upper 95% confidence interval will be less than or equal to the performance goal of 24.5%. For all the three cohorts, the analysis of the primary endpoint will be repeated for PP set as a secondary analysis.

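### At the planned 10% loss, the SAP 7.2 denominator gives less power than the stated 96% and 85%, because it keeps every event but drops event-free subjects lost before day 330

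*SAP*

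**What the plan says.** SAP 6.1 states that "an effective sample size of 369 subjects will yield 96% power to reject the null hypothesis", at a one-sided alpha of 0.05, a true rate of 11.3% and a goal of 17.5%. It then inflates to 410 for 10% loss. SAP 6.3 states that "an effective sample size of 180 subjects will yield 85% power to reject the null hypothesis", at a true rate of 16.3% and a goal of 24.5%, and inflates to 200. Protocol 14.2.1 and 14.2.3 say the same, and Protocol Table 9 repeats the 85% as a minimum.

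The decision in both cohorts is an exact binomial one-sided 95% upper limit compared with the goal (SAP 7.9.1.1 and 7.9.1.3). SAP 7.2 sets the inputs. The numerator is every ITT subject with an event by the time of interest. The denominator is "subjects who either have an event by the time of interest or have follow-up information beyond the lower window of the follow-up". SAP Appendix II puts the 12-month window at 360 ± 30 days, so the lower limit is day 330.

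Missing outcomes are handled only in supplementary analyses. In 7.9.1.3, "subjects who drop out prior to 330 days post-procedure and do not experience TVF will have their 12-month TVF-missing status" imputed by multiple imputation and examined by a tipping point analysis; 7.9.1.1 does the same for TLF. The Primary Cohort also has a survival analysis: "The upper bound of 95% confidence interval through 12 months will be used to compare to the performance goal of 17.5" per cent. The Bifurcation section has no such comparison with 24.5%.

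**The concern.** The power calculation assumes that loss removes subjects regardless of their outcome. The 7.2 rule does not. Take two subjects who leave at month six: the one who had a target-vessel MI at month two stays in both numerator and denominator, and the event-free one is removed. The analysed proportion is then higher than the true 12-month rate for which the test was powered.

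At stake is failure to meet the goal with a stent that performs exactly as expected, mainly in the smaller Bifurcation Cohort.

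A related gap concerns non-cardiac death before day 330 without TLF or TVF. The 12-month status is then known (no event), but there is no follow-up beyond day 330, so 7.2 read literally discards the subject. Protocol 10.14.1 says subjects "may be exited from the study for any of the following situations", and death is on that list. The rule for subjects who drop out before day 330 could therefore also be read to impute this known status.

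**Working it through.** **1. The plan's own figures.** Find the largest event count whose exact one-sided 95% upper limit is below the goal, then sum the binomial probability at the assumed true rate.

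- Primary, n = 369, goal 17.5%: at most 52 events (upper limit 17.4%; 53 events give 17.7%). Power at 11.3% is 95.9%.
- Bifurcation, n = 180, goal 24.5%: at most 34 events (upper limit 24.3%; 35 events give 24.9%). Power at 16.3% is 85.1%.

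Both stated figures reproduce.

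**2. The 7.2 rule.** Let p be the true 12-month rate, L the share lost before day 330 (assumed independent of outcome), and f the share of lost subjects' 12-month events that were seen before they left. Per subject:

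- P(event counted) = p(1 − L + Lf)
- P(event-free and counted) = (1 − p)(1 − L)
- Analysed rate = the first divided by the sum of the two

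The number evaluable is binomial with N = 410 or 200 and probability equal to that sum. Exact power is averaged over it. The documents give neither L beyond the 10% allowance nor f, so f runs over its full range; f = 0.5 is shown only as an assumption.

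Example for Bifurcation, L = 0.10, f = 1: 0.163 + 0.837 × 0.90 = 0.163 + 0.7533 = 0.9163. The expected number evaluable is 200 × 0.9163 = 183.3, and the analysed rate is 0.163 / 0.9163 = 17.8%. For Primary: 0.113 + 0.887 × 0.90 = 0.9113, so 373.6 evaluable and a rate of 12.4%.

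| Loss L | Bifurcation power, f = 0 / 0.5 / 1 | Primary power, f = 0 / 0.5 / 1 |
|---|---|---|
| 10% | 84.0% / 76.8% / 68.4% | 95.5% / 91.4% / 85.2% |
| 5% | 86.0% / 82.8% / 79.3% | 96.4% / 94.9% / 93.0% |
| 2% | 86.5% / 85.4% / 84.2% | 96.8% / 96.3% / 95.7% |

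At f = 0 and 10% loss there is no bias; the small drop from 85.1% to 84.0% comes from letting the evaluable number vary.

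**3. Type I error.** Setting p at the goal with L = 0.10 gives 4.3% to 0.7% (Primary) and 4.2% to 1.0% (Bifurcation) for f = 0 to 1. The rule is conservative.

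**4. If the historical rates already carry the rule.** Solve for the p that makes the analysed rate equal 11.3% or 16.3% at the historical loss, then apply 10% loss in this study.

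| Historical loss under the same rule | Bifurcation, f = 0.5 / 1 | Primary, f = 0.5 / 1 |
|---|---|---|
| 10% | 84.3% / 84.6% | 95.6% / 95.7% |
| 3% | 79.1% / 73.8% | 92.8% / 89.3% |

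Sharing the rule is not enough; the amount and timing of loss must also be similar.

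**5. What the historical table shows.** In SAP Table 1 (Protocol Table 8), the row "RAC (Resolute Arm) - single bifurcation treatment" gives 11.6% of 133, which lies between 15/133 (11.3%) and 16/133 (12.0%). The other RESOLUTE All-Comers row gives 12.2% of 136, between 16/136 (11.8%) and 17/136 (12.5%). Neither is a whole count over its N; 15/129 and 16/131 would fit, as would a Kaplan-Meier estimate. The unadjusted 15.3% for the third row does fit its full N (52/339). The table is therefore mixed and does not settle the question.

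**6. Non-cardiac deaths at the boundary.** 34 events in 178 give an upper limit of 24.60%, which fails. One more known non-event, 34 in 179, gives 24.47%, which passes. Over evaluable numbers from 170 to 199 such a flip is possible at six sizes (174, 178, 183, 187, 192 and 197). The average chance that one added non-event changes the result is 0.9% at a rate of 16.3% and 1.3% at 17.8%.

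**The case against.** The strongest reply is that no stated number is wrong. The plan claims power for an effective sample size, and for 369 and 180 evaluable subjects the figures are right. That stands. A reader might infer that the power was miscalculated, and step 1 shows it was not.

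Second, 10% is an allowance that follow-up may beat. Contact by phone or e-mail suffices (Protocol 10.1), late visits are used (10.3), and a subject is not lost to follow-up until the 36-month window has closed (10.14.3). That also stands. It would be wrong to say that power falls whatever the loss: at 2% the extra evaluable subjects offset the bias. It would be equally wrong to take 68% as the expected power, since it needs the full 10% loss and every lost subject's event seen first. But 10% is the loss on which the plan bases 369 and 180, so power at that loss is the relevant figure.

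Third, the historical rates may have used the same denominator. They may, but step 4 shows that this alone does not close the gap, and neither document gives the historical loss.

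Fourth, 16.3% is itself a planning judgement, with one arm adjusted from 15.3% to 13.9% and 3.3 points added for the MI definition. The largest shift here, 17.8 − 16.3 = 1.5 points, is within that kind of uncertainty. This limits the weight of the point without removing it.

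Finally, multiple imputation and tipping point analyses already cover Bifurcation, so the missing survival comparison is a small matter. The boundary flip from one non-cardiac death is improbable, and reading death as dropout is only a possible reading. Both points are fair. The denominator rule still needs one clear sentence.

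**Conclusion.** The point holds at the plan's own 10% loss. Under the 7.2 denominator, power is 68.4% to 84.0% for Bifurcation (stated 85%) and 85.2% to 95.5% for Primary (stated 96%). If half of lost subjects' events are seen first, it is about 77% and 91%. This rests on loss independent of outcome, on true rates of 11.3% and 16.3% free of loss, and on event timing that the documents do not give.

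The shortfall is smaller at 5% loss and negligible at 2%. It disappears if the historical rates carried the same rule with a similar amount and timing of loss. A reader might infer that the rule could produce a false success. It cannot under these assumptions, because type I error falls below 5%. Nor do the documents support a call for more subjects or different goals. Severity is minor to should-fix: a power statement that does not match the planned analysis, and a denominator that read literally discards some known non-events.

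**What to change.** Keep the exact test, both goals and the enrolment.

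1. In SAP 6.1 and 6.3, Protocol 14.2.1 and 14.2.3, and Protocol Table 9, label 96% and 85% as power for a fixed evaluable n. Add power under the 7.2 denominator at 10% loss as a range over dropout timing: Bifurcation 68% to 84%, Primary 85% to 95.5%. Label any central value as an assumption. This can be omitted only if the historical rates are shown to have used the same rule with similar loss. Cost: wording only.

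2. In SAP 7.2, before analysis, state that a subject who dies of a non-cardiac cause before day 330 without TLF or TVF is counted in the denominator as a known non-event and is not imputed under 7.9.1.1 or 7.9.1.3. The downside is that this changes the input to the decision test and slightly lowers the analysed rate, so it must be fixed beforehand. If a cohort's 12-month analysis has already been run, keep its denominator for the primary result, add this as a sensitivity analysis, and report it as Protocol 14.1 requires for deviations.

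3. Optional and supplementary: add to SAP 7.9.1.3 a survival-based one-sided 95% upper bound for TVF through 12 months, compared with 24.5%. It parallels the comparison in 7.9.1.1, which does not itself say whether its bound is one-sided. Cost: one further analysis, with no effect on the decision test.
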